### 12.2. Standard data derivation

#### 12.2.1. Date derivation

SAS date derived from a character date: In case day is missing, 15 is used. In case day and month are missing, 30 June is used.

The onset day for a safety event is the number of days between the last study vaccination and the onset/start date of the event (onset date – last study vaccination + 1). This is 1 for an event starting on the same day as a vaccination.

The duration of an event is expressed in days. It is computed irrespective of severity as end date – start date + 1. Therefore, duration is 1 day for an event starting and ending on the same day.

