## 4. ENDPOINTS

### 4.1. Primary endpoints

#### Reactogenicity and safety

- Occurrence of solicited local and general AEs after each vaccination:
  - Occurrence of solicited local AEs during a 7-day follow-up period (i.e. on the day of vaccination and 6 subsequent days) after each vaccine dose, in all vaccine groups.
  - Occurrence of solicited general AEs during a 7-day follow-up period (i.e. on the day of vaccination and 6 subsequent days) after each vaccine dose, in all vaccine groups.
- Occurrence of unsolicited AEs after each vaccination:
  - Occurrence of unsolicited AEs during a 28-day follow-up period (i.e. on the day of vaccination and 27 subsequent days) after each vaccine dose, in all vaccine groups.
- Occurrence of hematological and biochemical laboratory abnormalities after each vaccination:
  - Any hematological (red blood cells, white blood cells and differential count, platelets count and hemoglobin level) or biochemical (alanine aminotransferase, aspartate aminotransferase, creatinine, blood urea nitrogen [BUN] and BUN-to-creatinine ratio) laboratory abnormality at each visit subsequent to Day 1, in all vaccine groups.
- Occurrence of medically attended events (MAEs), potential immune-mediated diseases (pIMDs) and SAEs:
  - Occurrence of MAEs, pIMDs and SAEs throughout the entire study period, in all vaccine groups.

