2080.Vx	Subjects did not comply with vaccination schedule → Subjects that did not comply with the vaccination interval (including unknown dates): subjects for whom the dose 1→dose 2 is outside [56-66 days] subjects for whom the dose 2→dose 3 is outside [336-364 days]

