### 12.2.2. Dose number

The study dose number is defined in reference to the number of study visits at which vaccination occurred. More specifically dose 2 refers to all vaccines administered at the second vaccination visit while dose 3 corresponds to all vaccinations administered at the third vaccination visit even if dose 2 was not administered to the subject.

The relative dose for an event (AE, medication, vaccination) is the most recent study dose given before an event. In case the event takes place on the day a study dose is given, the related dose will be that of the study dose, even if the event actually took place before vaccination. For instance, if an adverse event begins on the day of the study vaccination but prior to administration of the vaccine, it will be assigned to this dose. In case a study dose is not administered and an event occurs after the subsequent study dose (e.g. 3rd study dose), the relative dose of the event will be study dose associated to the subsequent study dose (e.g. dose 3).

The number of doses for a product is the number of time the product was administered to a subject.

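### SAP 12.2.1 fills in a missing onset day without reference to the vaccination date, so a partially dated AE that began after a dose can be placed before it

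*SAP*

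**What the plan says.** SAP Amendment 3, Section 12.2.1, gives one rule for all incomplete dates: "In case day is missing, 15 is used. In case day and month are missing, 30 June is used". No condition is attached. The same section then says: "The onset day for a safety event is the number of days between the last study vaccination and the onset/start date of the event". The formula is onset date minus last study vaccination plus 1, and for the vaccination day itself "This is 1 for an event starting on the same day as a vaccination".

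Section 12.2.2 assigns the dose from the same date: "The relative dose for an event (AE, medication, vaccination) is the most recent study dose given before an event". Its special cases are an event on the day of a dose and a dose that was not given. Section 10 adds no further derivation rule and points back to Section 12.

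The endpoint that depends on these derivations is in Section 4.1: "Occurrence of unsolicited AEs during a 28-day follow-up period", counted as the vaccination day and the 27 days after it, for each dose. Under Section 12.2.5, a vaccinated subject with no reported event counts as a subject without one.

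**The concern.** The 15th and 30 June are chosen without looking at the vaccination date. If a subject is vaccinated on the 20th and an AE is recorded only by that month, the imputed onset is five days before the injection, even when the event followed it.

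At dose 1 such an AE has no preceding study dose. At doses 2 and 3 it is attributed to the previous dose, far beyond that dose's Day 28, so it is missing from both 28-day tables. Dose 2 is PBS in seven of the ten groups (Section 2), so in those groups an event that followed the Month 14 vaccination could be listed under a PBS injection. With 47 subjects per group, one misplaced subject moves a group percentage by 1/47 = 2.1 points. The dose and day-of-onset columns of the SAE and pIMD listings (Templates 21 and 22) would also be wrong for that event.

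**Working it through.** **Inputs from the SAP.** Imputation rule and onset-day formula (12.2.1); dose rule (12.2.2); window of Days 1-28 (4.1); intervals of 56-66 days from dose 1 to dose 2 and 336-364 days from dose 2 to dose 3 (5.2.2.2).

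**Assumptions, because the SAP gives no figure.** Vaccination dates are uniform over a 365-day year, and true onset is uniform over Days 1-28.

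**Check of the formula.** Onset on the vaccination day gives 0 + 1 = 1, as the SAP states.

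**Single cases.**
- Dose 20 January, true onset 24 January (Day 5), day missing: imputed 15 January, so 15 - 20 + 1 = Day -4, before the dose.
- Dose 10 January, true onset 3 February (Day 25), day missing: imputed 15 February = Day 37, after the window.
- Dose 10 October, true onset 14 October, only the year known: imputed 30 June = Day -101.

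**All combinations.** 365 vaccination dates x 28 onset days = 10,220.

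| Known part of date | Before dose | Days 1-28 | After Day 28 |
|---|---|---|---|
| Month and year, present rule | 1,523 (14.9%) | 7,437 (72.8%) | 1,260 (12.3%) |
| Month and year, floor at dose | 0 | 8,960 (87.7%) | 1,260 (12.3%) |
| Year only, present rule | 4,774 (46.7%) | 784 (7.7%) | 4,662 (45.6%) |
| Year only, floor at dose | 0 | 5,558 (54.4%) | 4,662 (45.6%) |

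The floor removes the first error and leaves the last column unchanged.

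**Where displaced events go (day missing).** Events pushed before dose 2 land on Days 41-66 after dose 1. Those pushed before dose 3 land on Days 321-364 after dose 2. Neither range touches a 28-day window.

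**Traffic in the other direction.** With a flat event rate per day and the day missing, in day-equivalents per 28-day window:
- Lost: 4.17 (placed before the dose) + 3.45 (placed after Day 28) = 7.62.
- Gained: 4.17 (true onset after Day 28) + 3.45 (true onset before the dose, same month) = 7.62.
- Doses 2 and 3: net zero.
- Dose 1, if events before dose 1 are not in the data: 7.62 - 4.17 = 3.45 lost, and 3.45/28 = 12.3%.

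**What the floor costs.** At doses 2 and 3, false inclusion of events that began before the dose rises from 3.45 to 14.72 day-equivalents. The higher figure is the average number of days in the vaccination month that precede the dose. It applies if no other record identifies such events as earlier.

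**The case against.** Section 12.2.1 is a generic rule for character dates, and the only date the SAP identifies as lacking a day is the date of birth (12.2.3). Nothing in the SAP shows that AE onset dates can be incomplete, and the final analysis is to use fully clean data (8.1), so the percentages may describe an empty or very small set. The safety analyses are descriptive and the rule is the same in all ten groups. Solicited symptoms are analysed from symptom screens per dose, and whole-study SAE counts do not depend on onset day. All of this stands and limits the practical weight of the point.

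A reader might add the two losses, 14.9% + 12.3% = 27.2%, and conclude that the missing floor makes the plan under-count AEs by that amount, in the non-conservative direction. The documents do not support this. The 12.3% comes from choosing the middle of the month, not from the missing floor. Under a flat event rate, gains equal losses at doses 2 and 3, and the net loss at dose 1 is 12.3%. A larger net loss needs AEs to cluster in Days 1-28. That is plausible after vaccination, but the SAP gives no figure for it.

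Nor is the floor free. For example, an event that truly began on 5 January in a subject given dose 2 on 20 January would become Day 1 of dose 2. That is a wrong attribution, though it errs towards ascribing the event to the new dose.

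**Conclusion.** The concern holds in a limited form. The written rule can place an AE that followed a dose before that dose, with the wrong relative dose or none, and remove it from a primary safety table. Assuming uniform vaccination dates and uniform true onset, this happens to 14.9% of true Day 1-28 AEs with the day missing and to 46.7% with day and month missing. The placements after Day 28 are a separate weakness that a floor does not cure.

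Misattribution follows from the rule itself whenever such dates occur. A net under-count is clear only for dose 1, or where AEs cluster after vaccination. How many AE onset dates are partial is unknown, so the effect on the reported tables may be small.

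**What to change.** Add to Section 12.2.1, for AE onset only: if the known month and year (or the known year) are those of a study vaccination, and nothing else recorded, such as the end date, shows that the event preceded the dose, impute the later of the present default and that vaccination date. Doses are at least 56 days apart under the planned schedule, so a month holds at most one. A calendar year can hold doses 1 and 2, so the text should name which applies when only the year is known, for example the first in that year.

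Flag and list the imputed onsets and report their number. Leave the present rule as it is for all other dates: birth, medication, vaccination and medical history still need it.

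State the downside in the SAP: at doses 2 and 3, some events that began earlier in the vaccination month will be attributed to the new dose, which is the conservative direction.

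The cost is a few lines in Annex 1 and in the derivation program. If there are no partial AE onset dates, one sentence saying so closes the point.

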### 12.2.2. Dose number

The study dose number is defined in reference to the number of study visits at which vaccination occurred. More specifically dose 2 refers to all vaccines administered at the second vaccination visit while dose 3 corresponds to all vaccinations administered at the third vaccination visit even if dose 2 was not administered to the subject.

The relative dose for an event (AE, medication, vaccination) is the most recent study dose given before an event. In case the event takes place on the day a study dose is given, the related dose will be that of the study dose, even if the event actually took place before vaccination. For instance, if an adverse event begins on the day of the study vaccination but prior to administration of the vaccine, it will be assigned to this dose. In case a study dose is not administered and an event occurs after the subsequent study dose (e.g. 3rd study dose), the relative dose of the event will be study dose associated to the subsequent study dose (e.g. dose 3).

The number of doses for a product is the number of time the product was administered to a subject.

### 12.2.3. Demography

Baseline measurements will be defined as the one closest to first vaccination date or on the date of first vaccination (but not later).

The age will be computed as the number of units between the date of birth and the reference activity. Note that as the day is not collected, the derived age may be incorrect by up to 1 month. This may lead to apparent inconsistency between the derived age and the eligibility criteria/the age category used for randomization.

Unit conversions for weight, height and temperature are done at the level of the SDTM data using the below rules:

- Conversion of weight to kg:
  - Weight in Kilogram = weight in Pounds \* 0.45359237
- Conversion of height to cm:
  - Height in Centimeters = Height in Inch \* 2.54.
- Conversion of temperature from °Fahrenheit to °Celsius
  - Temperature in °Celsius = ((Temperature in °Fahrenheit -32) \*5)/9

#### 12.2.4. Immunogenicity

For a given subject and given immunogenicity measurement, missing or non-evaluable measurements will not be replaced. Therefore, an analysis will exclude subjects with missing or non-evaluable measurements.

The GMTs calculations are performed by taking the anti-log of the mean of the log titer transformations. Antibody titers below the cut-off of the assay will be given an arbitrary value of half the cut-off of the assay for the purpose of GMT calculation. The cut-off value is defined by the laboratory before the analysis.

A seronegative subject is a subject whose antibody titer is below the cut-off value of the assay. A seropositive subject is a subject whose antibody titer is greater than or equal to the cut-off value of the assay.

For an assay with a specific 'cut-off', numerical immunological result is derived from a character field (rawres):

- if rawres is 'NEG' or '-' or '(-)', numeric result = cut-off/2,
- if rawres is 'POS' or '+' or '(+)', numeric result = cut-off,
- if rawres is '< value' and value  $\leq$  cut-off, numeric result = cut-off/2,
- if rawres is '< value' and value  $>$  cut-off, numeric result = value,
- if rawres is '> value' and value  $<$  cut-off, numeric result = cut-off/2,
- if rawres is '> value' and value  $\geq$  cut-off, numeric result = value,
- if rawres is ' $\leq$  value' or ' $\geq$  value' and value  $<$  cut-off, numeric result = cut-off/2,
- if rawres is ' $\leq$  value' or ' $\geq$  value' and value  $\geq$  cut-off, numeric result = value,
- if rawres is a value  $<$  cut-off, numeric result = cut-off/2,
- if rawres is a value  $\geq$  cut-off, numeric result = rawres,
- else numeric result is left blank.

The four-fold antibody titer increase, also called vaccine response rate (VRR), is defined as post vaccination titer/pre-vaccination titer  $\geq 4$  for pre-vaccination seropositive subjects; and post vaccination titer/half of the cut off value  $\geq 4$  for pre-vaccination seronegative subjects.

The ten-fold antibody titer increase is defined as post-vaccination titer/pre-vaccination titer  $\geq 10$  for pre-vaccination seropositive subjects; and post-vaccination/half of the cut off value  $\geq 10$  for pre-vaccination seronegative subjects.

MG is defined as the geometric mean of the pre- to post-vaccination titer fold increases.

SPR is defined as the percentage of subjects with serum HI titer  $\geq 1:40$ .

SCR is defined as the percentage of subjects with either a pre-vaccination HI titer  $< 1:10$  and a post-vaccination HI titer  $\geq 1:40$  or a pre-vaccination HI titer  $\geq 1:10$  and at least 4-fold increase in post-vaccination HI titer.

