## 2. STUDY DESIGN

\*If a subject presents signs and symptoms of influenza-like illness (ILI), nasal and throat swabs will be collected as soon as possible (preferably within 24 hours, but not later than 7 days) after the onset of an ILI to test for influenza and/or other respiratory pathogens by RT-PCR **if deemed necessary or for storage**.

\*\*IDMC reviews will be performed throughout the study.

- **Experimental design:** Phase I/II, observer-blind, randomized, controlled, multi-centric study with 10 parallel groups.
- **Study groups:**
  - **cH8/P/cH5-AS03 group:** 47 subjects receiving one dose of cH8/1N1+AS03 at Day 1, one dose of PBS at Day 57 and one booster dose of cH5/1N1+AS03 at Month 14.
  - **cH5/P/cH8-AS03 group:** 47 subjects receiving one dose of cH5/1N1+AS03 at Day 1, one dose of PBS at Day 57 and one booster dose of cH8/1N1+AS03 at Month 14.
  - **cH8/5/11-AS03 group:** 47 subjects receiving one dose of cH8/1N1+AS03 at Day 1, one dose cH5/1N1+AS03 at Day 57 and one booster dose of cH11/1N1+AS03 at Month 14.
  - **cH8/P/cH5-AS01 group:** 47 subjects receiving one dose of cH8/1N1+AS01 at Day 1, one dose of PBS at Day 57 and one booster dose of cH5/1N1+AS01 at Month 14.
  - **cH5/P/cH8-AS01 group:** 47 subjects receiving one dose of cH5/1N1+AS01 at Day 1, one dose of PBS at Day 57 and one booster dose of cH8/1N1+AS01 at Month 14.
  - **cH8/5/11-AS01 group:** 47 subjects receiving one dose of cH8/1N1+AS01 at Day 1, one dose cH5/1N1+AS01 at Day 57 and one booster dose of cH11/1N1+AS01 at Month 14.
  - **cH8/P/cH5 group:** 47 subjects receiving one dose of cH8/1N1 at Day 1, one dose of PBS at Day 57 and one booster dose of cH5/1N1 at Month 14.
  - **cH5/P/cH8 group:** 47 subjects receiving one dose of cH5/1N1 at Day 1, one dose of PBS at Day 57 and one booster dose of cH8/1N1 at Month 14.
  - **cH8/5/11 group:** 47 subjects receiving one dose of cH8/1N1 at Day 1, one dose cH5/1N1 at Day 57 and one booster dose of cH11/1N1 at Month 14.
  - **IIV4 group:** 47 subjects receiving one dose of *Fluarix Quadrivalent* at Day 1, one dose of PBS at Day 57 and one dose of *Fluarix Quadrivalent* at Month 14.
- **Treatment allocation:** randomized (1:1:1:1:1:1:1:1:1 ratio) using GSK Biologicals' Randomization System on Internet (SBIR). The randomization algorithm will use a minimization procedure accounting for center, sex, age (18-30 years vs. 31-39 years) and history of influenza vaccination since the 2014/2015 season (yes vs. no).

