### 6.2.2. Within group assessment

#### 6.2.2.1. Humoral immunogenicity assessment

For each study group, at each timepoint at which the tests are done and results are available, for each humoral immunity parameter, the following analyses will be performed:

- Seropositivity rates and GMTs, with exact 95% CI.
- MGI from Day 1, with 95% CI.
- MGI at Visits 10, 11 and 12 from Day 29 (=Visit 3), Day 85 (=Visit 6), Month 14 (=Visit 8), with 95% CI.
- Percentage of subjects with at least 4-fold increase from Day 1, with exact 95% CI (not applicable for HI test).
- Percentage of subjects with at least 10-fold increase from Day 1, with exact 95% CI (not applicable for HI test).
- Seroprotection rate (SPR) (only for HI test).
- Seroconversion rate (SCR) (only for HI test).
- Distribution of antibody concentrations using reverse cumulative distribution curves (only for ELISA test).

The correlation between anti-H1 HA stalk ELISA and anti-H1 HA stalk MN assay results will be explored.

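### A titre reported as below a limit that exceeds the cut-off is scored at that limit, so an HI result of `<40` counts as seroprotected

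*SAP*

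**What the plan says.** Section 12.2.4 lists how a reported result becomes a number for any assay with a cut-off. A result below a limit is set to half the cut-off only if that limit is at or below the cut-off. Otherwise the rule is "if rawres is '< value' and value $>$ cut-off, numeric result = value". No cut-off is given: "The cut-off value is defined by the laboratory before the analysis".

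The numeric result then feeds these definitions in the same section:

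- Seropositivity: "A seropositive subject is a subject whose antibody titer is greater than or equal to the cut-off value of the assay".
- Seroprotection: "SPR is defined as the percentage of subjects with serum HI titer" at or above 1:40.
- Seroconversion: "SCR is defined as the percentage of subjects with either a pre-vaccination HI titer" below 1:10 and a post-vaccination titre of at least 1:40, or a baseline of at least 1:10 and at least a four-fold increase.
- Four-fold response: "The four-fold antibody titer increase, also called vaccine response rate (VRR), is defined as post vaccination titer/pre-vaccination titer" of at least 4 if seropositive at baseline. If seronegative, half the cut-off is the denominator. The ten-fold response follows the same pattern.

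Section 6.2.2.1 limits the fold-rise rates to assays other than HI: "Percentage of subjects with at least 4-fold increase from Day 1, with exact 95% CI (not applicable for HI test"). For HI, the response measure is seroconversion. Nothing in Section 12.2.4 treats a result bounded above the cut-off differently for any of these endpoints.

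**The concern.** The limit in a result such as `<40` is the one value in its neighbourhood that the titre is known not to have reached. Substituting it puts the subject exactly on a threshold that the assay says was not met. Where the limit equals a response threshold, the subject is certainly misclassified. Where the limit is above the threshold, the subject is called a responder without evidence either way.

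The certain errors in the worked case fall on HI seroprotection and seroconversion, which are tertiary endpoints. The same derivation also supplies the ELISA and MN titres behind the primary and secondary seropositivity, GMT, MGI and fold-rise summaries, so the line should be correct even if it is rarely used.

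**Working it through.** The SAP states no figure that depends on this rule, so there is nothing to reproduce. The check passes bounded results through the rule as written and then applies the SAP's definitions.

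**Inputs.** Scoring rule, seropositivity, seroprotection, seroconversion and fold-rise definitions: Section 12.2.4. Group size 47: Section 2 ("47 subjects receiving one dose of cH8/1N1+AS03 at Day 1", and the same for the other groups). HI cut-off: assumed to be 10, from the 1:10 boundary in the seroconversion definition, with other values checked.

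**HI, post-vaccination result `<40`**

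| Cut-off | Scored as | Seropositive | Seroprotected | Seroconverted if baseline < 1:10 |
|---|---|---|---|---|
| 5 | 40 | yes | yes | yes |
| 10 | 40 | yes | yes | yes |
| 20 | 40 | yes | yes | yes |
| 39 | 40 | yes | yes | yes |
| 40 | 20 | no | no | no |

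With a baseline of 10, the scored ratio is 40/10 = 4, so the subject again counts as seroconverted.

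What a result below 40 can truly be at cut-off 10:

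| True titre | Seropositive | Seroprotected | Seroconverted (baseline < 1:10) | Seroconverted (baseline 10) |
|---|---|---|---|---|
| 5 | no | no | no | no |
| 10 | yes | no | no | no (1-fold) |
| 20 | yes | no | no | no (2-fold) |
| just under 40 | yes | no | no | no (just under 4-fold) |

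Seroprotection and both seroconversion cases are therefore certainly wrong under the rule. Seropositivity is undetermined.

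**ELISA and MN, subject seronegative at baseline.** With cut-off c, the denominator is c/2, so a four-fold rise needs 4 × c/2 = 2c and a ten-fold rise needs 10 × c/2 = 5c.

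- Post-vaccination limit exactly 2c (at c = 10, `<20`): scored 20/5 = 4, a four-fold responder. Every titre below 20 gives less than 4, so this is certainly wrong.
- Limit above 2c (at c = 10, `<40`): scored 40/5 = 8, a responder. A true 5 gives 1-fold and a true 20 gives 4-fold, so this is undetermined.
- Limit exactly 5c (`<50`): scored 50/5 = 10, a ten-fold responder, certainly wrong. Above 5c it is undetermined.

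**Bounded result at baseline.** At cut-off 10, `<40` scored as 40 makes the subject seropositive and requires 4 × 40 = 160 afterwards for a four-fold rise. A true baseline of 20 would need 80, and a true 5 would need 20. Here the error hides rises.

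**Size per group of 47, HI `<40` at cut-off 10.** For k such results, the seroprotection rate rises by 100 × k/47 points. The GMT rises by the factor (40/x)^(k/47), where x is the value that 40 is compared with.

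| k | Seroprotection rate | GMT against 20 (value/2): 2^(k/47) | GMT against 5 (cut-off/2): 8^(k/47) |
|---|---|---|---|
| 1 | +2.13 points | 1.015 | 1.045 |
| 3 | +6.38 points | 1.045 | 1.142 |
| 5 | +10.64 points | 1.077 | 1.248 |

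The rows for 3 and 5 are illustrations. The SAP gives no basis for any particular k.

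**The case against.** The strongest reply is that this is an edge case. Nothing in the SAP shows that a laboratory in this trial will report a limit above its own cut-off, and the certain errors shown for HI are confined to tertiary, descriptive endpoints. That stands, and it limits the point to a minor one. It does not make the rule right: the SAP wrote a specific line for this case, and the line gives a wrong answer when followed.

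A reader might also infer more than the document supports:

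- **That the line breaks the list's own convention of halving.** It does not. A result reported as at or below a limit that is itself at or above the cut-off is also taken at face value, and no rule in the list halves a reported limit. Half the cut-off is used for results resolved as below the cut-off.
- **That short serum volume makes such results likely.** The priority ranking in Section 2 governs the order in which assays are run. It says nothing about starting dilutions.
- **That every affected result is a known negative.** Only the cases where the limit equals the threshold are certain. Seropositivity, and fold rises with a higher limit, are undetermined.
- **That the GMT is inflated by 25%.** This needs five such results in one group, all truly at half the cut-off. Against half the reported limit, the same five give 7.7%.
- **That the adjuvant decision in Section 7 is affected.** ELISA titres pass through the same derivation, but nothing in the document shows an effect on that rule.

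**Conclusion.** The point holds, as a minor one. The rule scores a bounded result at its excluded upper limit. With an HI cut-off below 40, `<40` is counted as seroprotected, and as seroconverted from a baseline below 1:10 or equal to 10, when no possible titre qualifies. In ELISA and MN it makes a baseline-seronegative subject a four-fold responder wrongly at a limit of twice the cut-off, and without evidence above that.

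Each HI result of this kind moves the seroprotection rate by 2.1 points in a group of 47 and the GMT by 1.5% to 4.5%. This rests on three assumptions: an HI cut-off of 10 for the GMT range (any cut-off below 40 suffices for the seroprotection error), all 47 subjects evaluable, and at least one such result occurring. The frequency is unknown, so the total effect cannot be given. At a cut-off of 40 the `<40` example does not arise.

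**What to change.** Replace the line in Section 12.2.4 for a result below a limit that exceeds the cut-off with three statements:

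1. The result never counts as meeting a threshold at or above its limit, including a fold-rise threshold that would need at least that titre.
2. Where the limit does not settle seropositivity or a fold increase, that status is missing. This fits the section's existing principle that non-evaluable measurements are left out and not replaced.
3. For GMT and MGI, the number used lies below the limit: for example half the limit, or the point midway on the log scale between half the cut-off and the limit. For `<40` at cut-off 10 these are 20 and √(5 × 40) ≈ 14.1. Status is not derived from this number.

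The line for results at or below a limit need not change for seroprotection, since a titre reported as at most 40 can be 40.

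The cost is one derivation line and its programming. A few results may become non-evaluable for a rate.
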